#### **7.3.5.1 Pregnancies**

Any subject who becomes pregnant during the course of treatment will be instructed to immediately stop all treatments and will be discontinued from the study. Also, any subject who becomes pregnant in the two week period following their completion of the treatment phase of the study, or their discontinuation from the study (for reasons other than pregnancy), will be instructed to contact the clinic to report the pregnancy. All treated study subjects who report a pregnancy during the course of the trial will be followed during the course of their pregnancy by the study doctor to determine the outcome of the pregnancy.

### **7.3.6 Concomitant Medications**

The identity of all concomitant medications taken 30 days prior to enrollment into the study, 30 days prior to enrollment into the Treatment Phase of the study, and during the Treatment Phase of the study, as well as their total daily dose, duration of use, and

indication for use, will be reported on the case report form (CRF). Any possible exclusionary medication must have a stop date prior to eligibility for treatment.

### **7.3.7 Subject Return of Unused Test Material to the Clinic**

All subjects will be instructed to return their Treatment kit, with any unused test materials, to the clinical site on whichever is the first clinic visit following completion of all their treatments. The subjects should have disposed of the used swabs at home.

At the conclusion of the study, those subjects who have been enrolled, but never entered the Treatment Phase of the study, will be contacted and asked to return their unused Treatment kit. Should a subject not return their clinical trial material when requested, at least one additional phone call should be made, and, if necessary, a certified letter should be sent to request return of those materials. If these efforts are unsuccessful the subject's clinical trial materials will be considered missing. The return of both used study solution bottles and unused clinical trial materials is important with regard to drug accountability.

Study subjects who have entered the Treatment Phase of the study and administered their lesion treatment, will be offered compensation for bringing in their used clinical study solution bottle after completion of all their study treatments. This incentive is important as the immediate return of the materials to the clinic will minimize loss or misuse. Those subjects who forget to bring in their used clinical materials immediately after completion of all their study treatments will be offered a lower compensation to return the materials at a later date. Those subjects who were enrolled into the trial but did not enter the study Treatment Phase will be offered compensation for the return of all unused clinical trial materials at the termination of the study.

### **7.4 Follow-Up Telephone Assessment**

Two weeks, or up to 3 weeks, if there are scheduling issues, after the subject has completed the Treatment Phase of the study (complete healing of the herpetic episode or Visit Day 14, whichever is earlier) the clinic will contact the subject by phone for a final safety evaluation. Any new adverse events that have occurred since the subject's last clinic visit should be collected at this time.

## **8 ADVERSE EVENTS**

All adverse events occurring during the Treatment Phase of this clinical trial will be recorded on the case report form provided. Adverse events occurring before the onset of treatment will be classified as non-treatment emergent adverse events and will not be captured on the CRF. Adverse events occurring after the application of study treatment will be assigned as treatment emergent adverse events and will be recorded on the CRF. The Investigator will review each event and assess its relationship to the treatment (not related, unlikely, possible, probable and highly probable). The following definitions will be used for rating relationship to treatment:

- Not related – The event is clearly related to other factors such as the subject's clinical state, therapeutic interventions, or concomitant medications administered to the subject.
- Unlikely – The event was most likely produced by other factors such as the subject's clinical state, therapeutic interventions, or concomitant medications administered to the subject; **and** does not follow a known response pattern to the investigational product.
- Possible – The event follows a reasonable temporal sequence from the time of investigational product administration; **and/or** follows a known response pattern to the study treatment; **but** could have been produced by other factors such as the subject's clinical state, therapeutic interventions, or concomitant medications administered to the subject.
- Probable – The event follows a reasonable temporal sequence from the time of investigational product administration; **and** follows a known response pattern to the investigational product; **and** cannot be reasonably explained by other factors such as the subject's clinical state, therapeutic interventions, or concomitant medications administered to the subject.
- Highly Probable – The event follows a reasonable temporal sequence from the time of investigational product administration; **and** follows a known response pattern to the investigational product; **and** cannot be reasonably explained by other factors such as the subject's clinical state, therapeutic interventions, or concomitant medications administered to the subject; **and** either occurs immediately following investigational product administration, **or** improves on stopping the investigational product, **or** reappears on repeat exposure, **or** there is a positive reaction at the application site.

Each adverse event reported will be graded on a 3-point severity scale (mild, moderate, or severe) and the date and time of onset, time relationship to treatment, duration, and outcome of each event will be noted on the case report form.

The following definitions for rating severity will be used:

- Mild – easily tolerated, causing minimal discomfort and not interfering with normal everyday activities.
- Moderate – sufficiently discomforting to interfere with normal everyday activities.
- Severe – incapacitating and/or prevents normal everyday activities.

If any of the above adverse events are serious, as defined by the FDA Code of Federal Regulations (CFR), Title 21, special procedures will be followed. All serious adverse events will be reported within 24 hours by fax or e-mail to the Drug Safety Group at [contact], whether or not the serious events are deemed treatment-related. The

Drug Safety Group will notify Topical Remedy's Vice President of Clinical Research of the serious adverse event. All serious event reporting will adhere to 21 CFR 312.32 for IND drugs. The central IRB and other study sites will be notified by Topical Remedy, LLC of the Alert Reports per FDA regulations. Sites using their own institutional IRB will be instructed by Topical Remedy, LLC to notify their institutional IRB of the Alert Report.

The following is the definition for serious adverse events per FDA regulations:

A Serious Adverse Event is any adverse drug experience occurring at any dose that results in any of the following outcomes: death, a life-threatening adverse drug experience, in-patient hospitalization or prolongation of hospitalization, a persistent or significant disability/incapacity, or a congenital anomaly/birth defect. Important medical events that may or may not result in death, be life-threatening, or require hospitalization may be considered a serious adverse drug experience when, based upon appropriate medical judgment, they may jeopardize the subject or subject may require medical or surgical intervention to prevent one of the outcomes listed in this definition.

If a serious adverse event occurs to a subject on this study, the Investigator will complete the SAE form provided and fax it, along with the front cover sheet provided, to the Drug Safety Group at [contact]. The Medical Monitor will be responsible for ensuring completeness of the SAE form and for reviewing the SAE versus source documentation and the CRF.

Once the SAE form is complete, the Medical Monitor will forward it, by email, to the Vice President of Clinical Research at Topical Remedy (email: [contact]; [contact]) for review. The Vice President of Clinical Research will send any comments to Drug Safety. Drug Safety will track the SAE information and forward a desk copy of the complete SAE report to Topical Remedy, LLC.

Adverse events, whether serious or non-serious, will be followed to resolution or until the condition stabilizes, is otherwise explained, or the subject is lost to follow-up, up to a maximum of 30 days following the subject's last clinic visit. Adverse events, whether serious or non-serious, will be captured up to 2 weeks following the last clinic visit, and followed up to a maximum of 30 days following the subject's last clinic visit. Where appropriate, medical tests and examinations will be performed to document resolution of event(s). Outcome may be classified as resolved, improved, unchanged, worse, fatal, or unknown (lost to follow-up). Following the resolution of any study associated adverse events or after the completion of the Treatment Phase of the study, there will be no further adverse event reports for that subject.

While pregnancy itself is not considered to be an AE, any pregnancy complication or elective termination of a pregnancy for medical reasons will be recorded as an AE or SAE (as appropriate). A spontaneous abortion is always considered to be a SAE.

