A pilot clinical study (Protocol TR-H-111) was performed by the sponsor to investigate the potential skin irritancy of Merlin. The study involved the application in 40 subjects, of a total of thirty-six (36) treatments over four (4) days. More specifically, each subject administered three (3) applications of Merlin or placebo, depending on how a subject was randomized, twenty (20) minutes apart, for each set of treatments. These sets of treatments were repeated two (2) more times at six (6) and twelve (12) hour after the start of the initial treatments, for a total of nine (9) treatments of active or placebo on Day 1. The sets of treatments were then re-applied three (3) times each day for three (3)

additional days, resulting in the above noted total of four (4) days of treatment with thirty-six (36) applications of active or placebo.

On Day 1, scoring of the skin reaction was performed at the treatment site within 5 min prior to each initial application in a set of 3 applications, and within 5 minutes after the third application in the set of 3 applications. On Days 2 through 4, scoring of the treatment site was performed only for the first set of applications, when the subject was in the clinic for the first set of test article applications. Similarly to the timing for the evaluations on Day 1, scoring of the skin reaction in the treatment site was performed within 5 min prior to the initial application in the first set of 3 applications, and within 5 minutes after the third application in the first set of 3 applications. Skin reaction scoring on Day 5 was performed at 24 hours ( $\pm$  1 hour) from the time of the first treatment on Day 4. Any skin reactions noted on Day 5 were to be followed either with daily clinic visits or telephone contacts, as deemed appropriate, until the event was resolved.

The results of the skin irritation portion of the study revealed that all treatments were very well tolerated by all subjects, with no significant skin irritation and only a few, mild adverse events. Minimal erythema was the most notable reaction observed immediately after treatment in three subjects, and this resolved in all subjects within 1 hour. The only other reported adverse drug related adverse event was mild burning on treatment application in one subject; this also resolved rapidly.

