#### 5.3.1 Inclusion Criteria

1. Subject has a visible herpes simplex labialis lesion, in an area around the mouth, assessed by the subject, and confirmed by telephone contact, to be at the erythema stage (Stage 1) or Papule/Edema stage (Stage 2) as defined below:

**Stage 1:** **Erythema stage** is defined as any redness with no skin swelling or other signs of advanced stages.

**Stage 2: Papule/Edema stage** is defined as any skin swelling or solid raised area above the normal surface without evidence of more advanced stages such as fluid filled blisters.

2. Female subjects must be using a medically acceptable form of birth control during the study. Acceptable birth control measures include but are not limited to: abstinence, oral contraceptive pills or patch, injectable contraception, barrier contraceptives (condom, diaphragm with spermicide), IUD, vaginal contraceptive ring, surgical (hysterectomy, tubal ligation), vasectomized partner, and natural post-menopausal inability to conceive. Menopause is defined for this protocol as starting one year after the time of the last menstrual period.
3. Subject has immediate access to the kit containing the clinical trial material. (The subject will demonstrate access to the clinical trial material kit by reading the Randomization Number printed on the label on the kit.)
4. Subject is able to appear for a clinic visit within 24 hours from the time of enrollment into the Treatment Phase of the study (from the time the subject called to establish entry into the Treatment Phase of the study) and is able to return to the clinic for the full 14 day duration of the study if necessary.

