### **7.2.2 Lesion Assessment**

Subjects will have been trained at screening to recognize whether they are at the prodromal stage (Stage 0), the erythema stage (Stage 1), the papule/edema stage (Stage 2) or a more advanced herpetic stage, with particular attention to distinguishing between Stage 2 and any later stages. Only subjects with a lesion in Stage 1 or Stage 2, the early visible signs of a herpetic outbreak, will be entered into the Treatment Phase of the study and therefore allowed to treat themselves. Subjects reporting a more advanced herpetic lesion, beyond Stage 2, will be instructed that they are still in the study but must wait until their next lesion outbreak before again calling in to attempt to enter the Treatment Phase of the study. Subjects reporting a lesion in the prodromal stage, Stage 0, will be instructed to monitor their lesion for first visible signs of a cold sore, and followed as described above. If a subject has two or more distinct lesions, the subject will treat the first lesion that appeared as long as it has not progressed beyond Stage 2. If any lesions

have progressed beyond Stage 2, as noted above, the subject will be instructed to wait until their next outbreak before calling to enter the Treatment Phase of the study.

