## 7.12 Safety Data

The Safety Population will be used for all summaries of safety data. The safety analysis will be performed on the Safety Population. Assessment of safety and tolerability will be based on AEs. Each AE will be graded with respect to its relationship to treatment using five categories: not related, unlikely, possible, probable, and highly probable. Each AE will also be graded on a three-point severity scale: mild, moderate, and severe. AEs will be coded by body system and preferred term using the Medical Dictionary for Regulatory Activities (MedDRA).

The number and percentage of subjects experiencing treatment emergent adverse events (TEAE) will be tabulated for each treatment group by system organ class (SOC) and preferred term (PT). TEAEs are those occurring on or after first dose of study product. A subject having the same TEAE more than once over the course of the study will be counted only once in the incidence calculation for that TEAE. Similarly, if a subject had more than one TEAE in a SOC, the subject will be counted only once in the total number of subjects with TEAEs for that SOC. The number and percentage of subjects experiencing TEAEs will also be tabulated for those related to treatment (i.e., including possible, probable and highly probable), those that are severe, and those that are serious. If a TEAE is reported more than once for a subject, only the most related event will be counted in the summary for related TEAEs. For the summary of severe TEAEs, if a TEAE is reported more than once for a subject, only the most severe event will be counted in the summary. For the summary of serious TEAEs, if a TEAE is reported more than once for a subject, only the most serious event will be counted in the summary.

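### Treatment-emergent events are defined by timing alone with no worsening clause, so worsening of redness or swelling already present at the treated site can go unrecorded

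*Protocol*

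**What the plan says.** Protocol section 8 contains three sentences on capture. The first is general: "All adverse events occurring during the Treatment Phase of this clinical trial will be recorded on the case report form provided". The next two split events by time: "Adverse events occurring before the onset of treatment will be classified as non-treatment emergent adverse events and will not be captured on the CRF", and "Adverse events occurring after the application of study treatment will be assigned as treatment emergent adverse events and will be recorded on the CRF". SAP 7.12 uses the same split for the tables: "TEAEs are those occurring on or after first dose of study product". Neither document adds a clause for a sign that is present before the first application and then worsens.

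Protocol 7.2.2 sets the condition of the site at the start of the Treatment Phase: "Only subjects with a lesion in Stage 1 or Stage 2, the early visible signs of a herpetic outbreak, will be entered". Under Protocol 5.3.1, Stage 1 "is defined as any redness with no skin swelling or other signs of advanced stages", and Stage 2 "is defined as any skin swelling or solid raised area above the normal surface without evidence of more advanced stages". The solution is applied to that lesion (Protocol 7.2.4).

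On local reactions, Protocol section 2 reports from the pilot study: "Minimal erythema was the most notable reaction observed immediately after treatment in three subjects". It adds mild burning on application in one subject. Adverse events are the only safety endpoint (protocol synopsis; SAP 6.2).

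**The concern.** The main local reaction reported so far for this product, erythema, is the same sign that defines Stage 1, the earlier of the two stages at which a subject may start treatment. A timing-only rule works well when the site is normal at baseline. Here the site is red or swollen in every formally entered subject before the first application. An investigator who sees that redness deepen or the swelling increase has two defensible readings: a new event after treatment, which is recorded, or a sign that was there before treatment, which is not.

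Capture then depends on the investigator and on the site. If some worsening is left out, the count of local reactions is too low in both arms. If the same share m is lost in each arm, as blinding makes plausible, the recorded difference between arms is the true difference times (1 − m). Local tolerability matters for a pH 2.5 solution intended for over-the-counter use, and this trial has no other measure of it. The pilot scored skin reactions before and after application sets; no such score is planned here.

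**Working it through.** The documents state no planned rate or precision for local reactions, so there is no figure to reproduce. The check is mainly of the text.

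**1. Is there a worsening clause anywhere?** I read every place that defines, elicits, follows or tabulates adverse events: Protocol 7.3.5, 7.4, 8, 10.3.1 and 10.6, and SAP 6.2, 7.1.1 and 7.12. None mentions an increase in severity of a sign already present. Protocol 7.3.1 says when a secondary lesion may be an adverse event, but gives no corresponding rule for irritation at the treated site.

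**2. How would specific reactions be handled under the current wording?**
- Burning or stinging on application: a new event, timed to dosing. It qualifies.
- Redness on skin that was normal before treatment: new. It qualifies.
- Stage 1 redness that becomes more intense: not settled. The site was already red, and staging has no intensity grade, so the lesion stays at Stage 1.
- Swelling that appears in a Stage 1 lesion: not settled. It reads as progression to Stage 2.
- Stage 2 swelling that increases: not settled, for the same reasons.

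The ambiguity is confined to redness and swelling within the lesion area.

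**3. What baseline exists?** Lesion stage is assessed by the subject before first treatment (Protocol Table 7-1, footnote 5). Pain onset and severity are asked at the entry call (7.2.5.1), and stage and pain go in the diary before each treatment (7.2.5). Lesion dimensions are measured at clinic visits (7.3.3), which typically begin after treatment has started (Table 7-1, footnote 4). The intensity of redness or swelling before the first application is not recorded.

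**4. Scale, for illustration only.** Inputs: 3 pilot subjects with erythema and 40 pilot subjects across Merlin and placebo (Protocol section 2, split by arm not given); at least 75 treated subjects per arm (Protocol 5.1). The figure of 20 pilot subjects on Merlin is an assumption.
- All 40 as denominator: 3/40 = 7.5% (exact 95% CI 1.6% to 20.4%); 75 × 0.075 = 5.6 subjects.
- All three among an assumed 20 on Merlin: 3/20 = 15% (exact 95% CI 3.2% to 37.9%); 75 × 0.15 = 11.3 subjects.

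With a share m lost, the recorded number is 75 × rate × (1 − m):
- m = 0: 5.6 to 11.3
- m = 0.5: 2.8 to 5.6
- m = 1: 0

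The documents give no basis for choosing m. The pilot was in healthy subjects (Protocol section 4), so carrying its rate over to worsening on a lesion is a further assumption.

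**The case against.** The strongest reply is that the rule excludes less than it may seem to. The text says 'occurring', not 'starting'. Protocol section 8 opens by requiring all adverse events in the Treatment Phase to be recorded, and the entry lesion is the indication; the documents never call it an adverse event. A reaction to an application occurs after that application, so an investigator may record it as the text stands. The causality scale also has room for it: the top category names a positive reaction at the application site, 'possible' covers events that the subject's own condition could explain, and SAP 7.12 counts 'possible' as related. The previous Phase 2 study, in subjects with lesions, did report treatment-related events, although its event definition is not shown.

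This stands as far as it goes: loss is possible, not required. It does not remove the gap. Causality ratings apply only once an event has been recorded. Section 8 also asks for a date and time of onset for each event, which pulls the reading of 'occurring' towards onset.

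Four stronger readings are tempting, and the documents do not support them.
- A reader might infer that anything that began before treatment must be dropped. The wording allows this but does not require it.
- A reader might infer that irritation is an expected effect of Merlin. The pilot reports no significant irritation, and the minimal erythema resolved within 1 hour.
- A reader might infer that there is no baseline at all. Stage and pain have one, and skin conditions in the lesion area that could affect its course or evaluation are excluded at the entry call (5.3.2, criterion 9).
- A reader might assume zero recorded events in 75 and quote the one-sided 95% upper bound, 1 − 0.05^(1/75) = 3.9%. That needs total loss, which is only the extreme of the range.

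**Conclusion.** The point holds in a limited form. Both documents sort adverse events by timing alone, pre-treatment events stay off the CRF, and nothing says that worsening of an existing sign counts. Since formal entry requires redness or swelling at the application site, treatment-related worsening of those two signs within the lesion area can be left unrecorded. Burning and other clearly new events are not affected.

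The size is not known. On the pilot-based illustration, about 6 to 11 of 75 Merlin subjects might have a local reaction of this kind, and between none and all of them could be lost. This rests on the pilot's three cases, on an assumed 20 Merlin subjects for the upper figure, and on pilot rates applying to lesions. 'Every subject' means those formally entered: the safety population can also include people who treated themselves without authorization (Protocol 10.3.1), whose lesion stage is not fixed. No formal safety test is planned (SAP 7.1.1, 7.2), so the effect is on the descriptive tables and the tolerability conclusion, not on any error rate. It is worth correcting because the change is small and adverse events are the only safety endpoint.

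**What to change.** Make three changes.

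1. In Protocol section 8 and SAP 7.12, define a treatment-emergent adverse event as one that starts, or increases in severity, on or after the first application.
2. In Protocol section 8, state that a local reaction following an application is recorded as an adverse event unless it is the lesion's normal progression through the stages. Progression itself remains an efficacy measure.
3. On the entry-call form, note existing local signs (redness, swelling and their intensity as the subject reports them) as the baseline for judging worsening.

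The cost is about two sentences across the two documents and one or two lines on a form. Sample size, the efficacy analysis and treatment are unchanged. The downside is somewhat more low-grade local events in both arms, some due to the disease. The placebo arm calibrates these, since its subjects have the same lesions and are assessed under the same rule.

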Merlin, therefore, appears to be safe as the only reported adverse events were very mild skin irritation in three subjects and mild burning on application in one subject.

This was followed by Phase 2 study (TR-H-211) the primary objective of which was to assess the efficacy of Merlin as compared to a placebo treatment, on the clinician assessed duration to complete healing of the herpetic episode. Other endpoints included the clinician assessed: 1) prevention of progression to a classical lesion associated with herpes labialis; 2) duration of classical herpetic lesions; and 3) duration of the herpetic episode. The safety of Merlin was also evaluated.

A total of 469 subjects were enrolled in the study with 172 subjects actually treated. After being enrolled and randomized into the study, subjects were sent home with a kit containing a bottle filled with either Merlin (active) or the 10% ethanol placebo solution and a packet of foam-tipped applicators sufficient to apply three study treatments (nine (9) applications). The subject was instructed to contact the clinic by telephone at the first signs and/or symptoms of a recurrent herpetic episode (Stage 0 or 1, prodromal or erythema). The lesion then was confirmed by telephone interview with the subject, and upon confirmation of the lesion, the subject was instructed to begin treatment immediately, thereby initiating the Treatment Phase of the study. The subject was told to continue treatment for the remainder of the day with the treatment schedule as described above for the Phase 1 study, and to continue to treat with a set of three (3) treatments, three times each day, for a total of twelve (12) sets of treatments resulting in thirty-six (36) applications in total. The subject also was instructed to return to the clinic within 24 hours of the initial treatment for evaluation of the stage of the herpetic lesion.

Subjects reported daily for a minimum of 3 consecutive days, with the last clinic visit at the time of complete healing (Stage 7 - normal skin) or at 14 days, whichever is earlier. Subjects will be contacted by phone, for a safety assessment, 2 weeks after they complete the Treatment Phase of the study.

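### The causality scale in Protocol Section 8 has no category for a well-timed, otherwise unexplained reaction that is not already known

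*Protocol*

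**What the plan says.** Protocol Section 8 defines five levels of relationship to treatment for the investigator to apply to each event.

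- Not related: "The event is clearly related to other factors such as the subject's clinical state".
- Unlikely: "The event was most likely produced by other factors such as the subject's clinical state", and in addition the event "does not follow a known response pattern to the investigational product".
- Possible: a reasonable temporal sequence and/or a known response pattern, with the qualification that the event "could have been produced by other factors such as the subject's clinical state".
- Probable: a reasonable temporal sequence, and the event "follows a known response pattern to the investigational product", and no reasonable explanation by other factors.
- Highly Probable: everything in Probable, plus at least one extra feature (immediate onset, improvement on stopping, return on repeat exposure, or an application-site reaction).

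Protocol 10.6 tabulates adverse events by relationship to treatment. SAP 7.12 instead forms one related subset, tabulating treatment-emergent events for "those related to treatment (i.e., including possible, probable and highly probable", and SAP Section 10 lists a table on that subset by system organ class and preferred term. SAP Section 8 says that missing data will be queried and that missing safety data will not be imputed.

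**The concern.** Adverse events are the only safety endpoint (SAP 6.2), and Merlin is described as a novel formulation intended for over-the-counter sale (Protocol Section 2). A causality scale in this setting should be able to record a reaction that nobody has seen before.

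Here the two highest ratings are open only to reactions already recognised, and the one lower rating that counts as related is closed to an event with no plausible alternative cause. The ordering is perverse. A new, well-timed reaction with a plausible alternative cause is Possible and is counted as related. The same reaction with no plausible alternative cause has no category. At stake is whether the related-event table reflects such reactions, and at what level the protocol's tabulation by relationship shows them.

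**Working it through.** The plan states no figure to reproduce. The check applies the five written definitions to one event profile and then to all profiles.

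**Step 1: the disputed profile.** Temporal sequence reasonable; known pattern absent; other factors cannot reasonably explain the event.

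| Category | Binding requirement | Met? |
|---|---|---|
| Not related | Other factors clearly the cause | No |
| Unlikely | Other factors most likely the cause, and no known pattern | No: first condition fails |
| Possible | Temporal sequence and/or known pattern, but other factors could be the cause | No: second condition fails |
| Probable | Temporal sequence, and known pattern, and no other explanation | No: known pattern fails |
| Highly Probable | As Probable, plus one extra feature | No: known pattern fails |

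The result is 0 of 5, with or without an extra feature. With a known pattern present, the same event meets Probable, and also Highly Probable if an extra feature is present. The known-pattern clause alone makes the difference.

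**Step 2: all profiles.** Four inputs were varied: temporal sequence (yes/no), known pattern (yes/no), role of other factors (clearly / most likely / could / cannot explain) and extra feature (yes/no). This gives 2 × 2 × 4 × 2 = 32 combinations. A stronger attribution to other factors was taken to satisfy a weaker one, so an event clearly due to other factors also satisfies the could-have-been condition. The combinations meeting no definition are:

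| Temporal sequence | Known pattern | Other factors | Combinations (extra feature yes/no) |
|---|---|---|---|
| Yes | No | Cannot explain | 2 |
| No | Yes | Cannot explain | 2 |
| No | No | Could | 2 |
| No | No | Cannot explain | 2 |

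The total is 8 of 32. The first row is the one of concern; the other six combinations all lack a reasonable temporal sequence. These are counts of logical combinations, not estimates of how often such events occur.

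**Step 3: consequence of each available rating for the first row.**

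- Possible: inside the SAP 7.12 related set, so the event stays in the related table. In the Protocol 10.6 tabulation it appears one or two levels lower than the same event with a known pattern.
- Unlikely: outside the related set, so the event is absent from the related table.
- Blank: queried, but if unresolved it is not imputed, so it is also absent.

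**Step 4: test of the change.** If the known-pattern condition is removed from Probable and Highly Probable, the first row rates Probable, or Highly Probable with an extra feature. The uncategorised combinations fall to 8 − 2 = 6. If the clause is instead joined by and/or to the temporal sequence, as in Possible, the second row also gains a category and 6 − 2 = 4 remain.

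**The case against.** The strongest case on the other side accepts the gap in the wording and disputes its consequences. Most of that case stands.

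- A reader might infer that the wording pushes such an event to Unlikely, because that is the only definition that mentions absence of a known pattern. The documents do not support this as a prediction. Unlikely also requires other factors to be the most likely cause, which contradicts the profile outright. Possible fails only on its could-have-been clause, and an investigator may well choose it. The related table would then keep the event, and because it pools three categories, rating it Possible would change nothing there.
- A reader might also infer that the known pattern for Merlin is only erythema and burning, so that most new reactions would fall into the gap. The pilot study is indeed summarised as "the only reported adverse events were very mild skin irritation in three subjects and mild burning on application in one subject". But Protocol Section 2 says that both ingredients have known side-effect profiles and that the previous Phase 2 study, with 172 treated subjects, had treatment-related events, which it does not itemise. Protocol 5.4.4 adds sun sensitivity, and Protocol 11.2 refers to an Investigator Brochure that is not among these documents. How narrow the known pattern is cannot be settled from them.
- Safeguards do not depend on the rating. SAP 7.12 and Section 10 tabulate all treatment-emergent events by arm, system organ class and preferred term, which in a randomised placebo-controlled trial allows comparison without investigator attribution. Listings cover the Safety Population (SAP 7.2). Serious events are reported within 24 hours whatever their causality (Protocol Section 8). SAP 7.1.1 and 7.2 plan no inferential safety test.

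What remains is a rule that gives no answer for one coherent and clinically plausible profile, feeding a listed table, with no default in either document.

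**Conclusion.** The gap is real and follows from the text alone: a well-timed reaction with no reasonable alternative cause and no known pattern meets none of the five definitions, and supporting evidence on stopping or re-exposure cannot change that. It must be rated against a definition it does not meet. It may therefore be understated in the protocol's tabulation by relationship or missing from the SAP's related-event table.

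The point is minor. It affects descriptive causality tables only; no efficacy result, error rate or all-event safety table is touched, and no reaction disappears from the record. The documents give no count of affected events, so the size cannot be put in numbers. The conclusion assumes that the definitions are applied as written and that no rating guide outside these documents supplies a default.

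**What to change.** In Protocol Section 8, make the known response pattern non-mandatory in Probable and Highly Probable, either by deleting it as a condition or by using the and/or construction that Possible already has. An event with a reasonable temporal sequence and no reasonable alternative explanation would then be at least Probable, and Highly Probable when one of the listed extra features is present. If and/or is used, decide whether a known pattern without a reasonable temporal sequence should also qualify, since that wording would allow it.

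Add a default to SAP 7.12: an event that meets no definition is counted as related in the related-event table. After the wording change, this default would act only on the remaining profiles without a reasonable temporal sequence. If it is also to cover ratings still blank after query, align it with the no-imputation statement in SAP Section 8.

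The cost is a short amendment to Section 8, matching CRF guidance and one sentence in the SAP. The downside is that a few events may be rated or counted as more related than under the current text.
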